6 SCHEDULE OF EVENTS

PROCEDURES	Pre-surgery visit 2-4 weeks pre-surgery	Before surgery	Preadmission visit	While inpatient 6 to 10 days	Discharge visit	During follow-up	Post-surgery outpatient visit 2 month post-surgery	Post-surgery outpatient visit 6 months post-surgery
Informed consent	X							
Body measurements ¹	X				X		X	X
Baseline questionnaire	X							
SOC questionnaire	X							
Eligibility review	X							
Randomization	X							
PROMIS	X ²				X		X	X
Follow-up questionnaires ⁷					X		X	X
AM-PAC outpatient form	X				X		X	X
6MW test	X				X		X	X
Short Physical Performance Battery	X				X		X	X
Correlative blood collection (optional)			X				X	
Saliva sample (optional)								X
7 Day Physical Activity Recall	X						X	X

Protocol name: Precision Exercise Prescription Randomized Clinical Trial
Version Date: 24NOV2021
Previous Version: 16JUN2021
Principal Investigator: [name], PT

NCCN Distress Thermometer	X							
† PEP materials distribution ³	X				X		(X ⁶)	(X ⁶)
† PEP intervention (with PT)	X						X	X
† PEP intervention (home based)		Daily				Daily between visits		
† PT assessment + activity review	X ⁴			X ⁵	X ⁶		X ⁶	X ⁶
† Study team phone call + activity review ⁷ (PT adjust weekly exercises if needed)		Weekly				Weekly ⁶		

† **Only due for patients participating in the PEP intervention**

1. Body measurements will include height, weight, waist and hips measurements. Participants may receive these results if they are interested.
2. PROMIS is a clinic-based evaluation. Study staff will be obtaining this more frequently than required by clinic for the purposes of the study.
3. Materials include an exercise packet (with exercise tool), diary/calendar, and activity tracker at baseline and new tracking diary/calendars at the follow-up visits.
Participants may receive their exercise diary results if they are interested.
4. There will be no activity review at baseline (no activity started) and during the inpatient stay or at discharge (since the PEP intervention is on hold).
5. While inpatient the physical therapist will assess the patient (including AM-PAC scoring) as needed depending on the patient's condition.
6. Activity review + AM-PAC scoring *could* lead to an adjustment in exercise mode / dosage as well as the patient being given a new version of the tracking diary.
7. See details in Section 7.

7 QUESTIONNAIRES

7.1 Standard Questionnaires

The listed questionnaires below with their included questionnaire instruments may be given to all participants in the study. However, in instances when it isn't feasible to give a participant one of these standard questionnaires, a short form questionnaire (listed in 7.2.) will be provided in clinic or given to the participant to take home. The short form questionnaires may also be given to participants who have stated the questionnaires are time consuming or for participants who have not completed previous study questionnaires. Questionnaires may be sent via email, mail, or the participant's electronic medical record (MyChart).

Concept/ Instruments	# of Items	Standard of Care (-2)	Pre-surgery (-1)	Discharge (1)	2 month (2)	6 month (3)
1. Physical activity/ Motivation						
2. BREQ-3	24	24		24	24	24
3. 7-day physical activity recall phone interview	12		12		12	12
4. 7-day physical activity recall phone interview calendar	N/A		X		X	X
5. PEP Exercise Diary	N/A		X	X	X	X
6. Overall Health						
7. FACT-L	36		36	36	36	36
8. Sleep						

Protocol name: Precision Exercise Prescription Randomized Clinical Trial
Version Date:24NOV2021
Previous Version: 16JUN2021
Principal Investigator: [name], PT

9. PSQI (Pittsburgh sleep quality index)	10		10	10	10	10
10. Function						
11. AM-PAC outpatient short form	12		12	12	12	12
12. Activities of daily life (in WHI lifestyle questionnaire)	7		7		7	7
13. Lifestyle						
14. Diet						
15. DHQII (NCI last update 2017), past months with portion size	153				153	
16. Personal Habits						
17. Weight change	2		2			
18. Physical activity/ exercise, asks about the usual physical activity and exercise	3		3		3	3
19. Marijuana – ColoCare Q	1				1	
20. Smoking history	11		11			
21. Smoking follow-up	11				11	11
22. Exercise confidence	11				11	
23. Social Activities	6		6			

24. Religion and Spirituality	4		4			
25. Self-Efficacy						
26. Self-Efficacy (Sallis, [name] recommended)	12	12		12	12	12
27. Affect						
28. Modified Differential Emotion Scale (mDES), Emotion experience during the past 24 hours	20	20		20	20	20
29. Emotion WHI, asks about emotions in the past week	12		12			12
30. Social factors						
31. Social Support for Exercise (Sallis)	13	13		13	13	13
32. Subjective Social Status Ladders	2		1 out of 2		1 out of 2	1 out of 2
33. Financial Strain – COST	8		8			8
34. Benefit finding – ColoCare Q	17					17
35. Loneliness (Cacioppo)	3	3		3	3	3
36. Demographics						
37. Education – ColoCare Q	1		1			
38. Marital Status – ColoCare Q	1		1			

Protocol name: Precision Exercise Prescription Randomized Clinical Trial
Version Date:24NOV2021
Previous Version: 16JUN2021
Principal Investigator: [name], PT

39. Income – ColoCare Q	1		1			
40. Weight	2		2		2	2
41. Height-ColoCare Q	1		1			
42. Ethnicity	3		3			
43. Sex	1		1			
44. Birthday	1		1			

45. Cancer treatment distress scale						
46. CTXD	23				23	23
47. Symptoms						
48. Pain	1	1	1	1	1	1
49. Shortness of breath	1	1		1		
50. Fatigue (FACIT-F)	13		13	13	13	13
51. Living condition (nursing home, relationship etc.)						
52. WHI – Lifestyle questionnaire	3		3		3	3
53. Others						
54. PROMIS Score (Dimensions)	CAT	Clinic-based assessment				

Protocol name: Precision Exercise Prescription Randomized Clinical Trial
Version Date: 24NOV2021
Previous Version: 16JUN2021
Principal Investigator: [name], PT

55. Saliva Questionnaire	9					9
56. Blood Questionnaire	5		5		5	
57. Health Care Experience	9				9	9
58. Feedback Questionnaire	17					17
59. COVID-19		Completed as needed during outbreak				

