1.2 Secondary Objectives

1.2.1 Evaluate the improvement in strength, endurance, and balance.

Secondary Endpoint #1: Short Physical Performance Battery (SPPB) test scores

1.2.2 Gather patient-reported outcomes regarding disease-specific symptoms, multidimensional fatigue, common mental health issues, and hypothesized treatment mechanisms and evaluate differences between arms.

Secondary Endpoint #2: results from PROMIS, FACT-L (Functional Assessment of Cancer Therapy-Lung), FACIT-F (Chronic Illness Fatigue Scale), PSQI (Pittsburgh Sleep Quality Index), BREQ-3 (Behavioral Regulation in Exercise Questionnaire 3), AM-PAC outpatient short form, activity/exercise, tobacco history, mDES, WHI emotions, loneliness, and Subjective Social Status Ladders questionnaires.

Further secondary endpoints to be explored include self-efficacy, social support, disease-related symptoms (e.g., pain, shortness of breath, fatigue), activities of daily life, personal habits, emotions, exercise diaries, demographics, 7-day physical activity recall, background information, diet (measured by the DHQII from the NCI), cancer treatment distress (CTXD) and living conditions.

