9.2 Patient Reported Outcomes

Questionnaires aimed at measuring disease specific symptoms, multidimensional fatigue, common mental health issues (i.e., depression, anxiety, and alcohol use), and hypothesized treatment mechanisms will be obtained on this study at baseline, at discharge, and at the 2 and 6 months follow-up. The effect of the PEP intervention on patient reported outcomes will be evaluated by comparison between each arm of the study.

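### The dedicated shortness-of-breath item is not scheduled at 2 or 6 months, although 1.2.2 names the symptom among endpoints to be explored and 9.2 places symptom questionnaires at both visits

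*Combined protocol and SAP*

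**What the plan says.** Three parts of the combined protocol and SAP bear on this point.

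- **Section 1.2.2 (secondary objectives).** After the instruments listed under Secondary Endpoint #2, the text continues: "Further secondary endpoints to be explored include self-efficacy, social support, disease-related symptoms (e.g., pain, shortness of breath, fatigue", followed by further topics. Shortness of breath is one of three example symptoms. No instrument or time point is attached to it there.
- **Section 9.2 (patient-reported outcomes).** "Questionnaires aimed at measuring disease specific symptoms, multidimensional fatigue, common mental health issues" and hypothesized mechanisms "will be obtained on this study at baseline, at discharge, and at the 2 and 6 months follow-up". The use is then stated: "The effect of the PEP intervention on patient reported outcomes will be evaluated by comparison between each arm of the study".
- **Sections 7.1 and 7.2 (standard and short-form questionnaires).** Row 49, "Shortness of breath", is a one-item question. In both tables it has a count under Standard of Care and under Discharge. The cells for pre-surgery, 2 months and 6 months are empty.

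**The concern.** Section 1.2.2 names three symptoms together, and 9.2 says symptom questionnaires are collected at four time points so that the arms can be compared. A reader would expect all three symptoms at the 2-month and 6-month visits. Two of them are there. The only row labelled with the third is not, in either form of the questionnaire, and no reason is given.

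At stake is whether the trial can say anything about breathlessness from its own dedicated question once patients are past the early post-surgical period. The one post-surgery value is also loosely timed. Section 8.5 allows the discharge visit 1 to 8 weeks after the patient leaves hospital, with the window extendable, and lets the discharge questionnaire be completed as late as the 2-month visit. If the gap is found only at analysis, the team would have to choose a substitute measure of breathlessness after the data are in.

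**Working it through.** No sample size, power or error-rate figure bears on this point, so the check is a reading of the schedule.

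**Step 1: are the blanks real?** The header in 7.1 has seven columns (instrument, number of items, and five time points). The rows for pain, shortness of breath, FACIT-F and FACT-L each split into exactly seven fields, so the empty cells in row 49 are not caused by shifted columns. Section 7.2 has the same blanks in the same row.

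**Step 2: the three named symptoms and FACT-L** (same in 7.1 and 7.2; a dash is an empty cell)

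| Row | Standard of Care | Pre-surgery | Discharge | 2 months | 6 months | Columns filled | Of the 2- and 6-month visits |
|---|---|---|---|---|---|---|---|
| 48 Pain | 1 | 1 | 1 | 1 | 1 | 5 of 5 | 2 of 2 |
| 49 Shortness of breath | 1 | – | 1 | – | – | 2 of 5 | 0 of 2 |
| 50 Fatigue (FACIT-F) | – | 13 | 13 | 13 | 13 | 4 of 5 | 2 of 2 |
| 7 FACT-L | – | 36 | 36 | 36 | 36 | 4 of 5 | 2 of 2 |

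**Step 3: does row 49 follow a pattern used elsewhere in 7.1?**

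- Rows with an item count under Standard of Care: BREQ-3, self-efficacy, mDES, social support for exercise, loneliness, pain, shortness of breath. That is 7 rows. Six are repeated at both 2 and 6 months; 7 − 6 = 1 exception, shortness of breath.
- Rows with an entry at discharge: the six just mentioned, plus the exercise diary, FACT-L, PSQI, the AM-PAC short form, FACIT-F and shortness of breath. That is 6 + 6 = 12 rows. Eleven are repeated at both later visits; 12 − 11 = 1 exception, again shortness of breath.

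**Step 4: could burden explain it?** The documents do not say so. It is one question, and the short form in 7.2, meant for patients who find the questionnaires long, still asks 36 FACT-L items and 13 FACIT-F items at both visits.

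**Step 5: what remains possible.** A Standard of Care value and a discharge value are scheduled, so the arms can be compared at discharge with adjustment for the earlier value. With no value scheduled at 2 or 6 months, the item supports no comparison at either visit.

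**The case against.** The strongest reply has four parts.

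1. **The endpoint is lightly specified.** Shortness of breath appears only as an example within endpoints to be explored. It has no time point or test of its own and is not among the instruments of Secondary Endpoint #2. This stands and limits the weight of the point.
2. **Section 9.2 speaks of a category.** It promises questionnaires on disease-specific symptoms, not every item at every visit, and it does not mention breathlessness. FACT-L, FACIT-F, pain and PROMIS are all collected at 2 and 6 months, so the promise can be read as kept at category level. Other measures also depart from the four-time pattern: DHQII is at 2 months only, CTXD at 2 and 6 months only, and WHI emotions and COST at pre-surgery and 6 months. This stands in part: variation between rows is normal in these tables, and the sparse schedule may be deliberate. It does not explain why one of three symptoms named together stops after discharge when every other row collected at discharge goes on.
3. **Breathlessness may be measured elsewhere.** A reader might infer that the trial cannot compare the arms on breathlessness at all at 2 or 6 months. The documents do not support that. They do not list the items of FACT-L or PROMIS, so they neither show nor rule out another source. Equally, they do not say that either instrument supplies this endpoint.
4. **The primary analysis is untouched.** A reader might see the blank at 2 months as a gap in the primary analysis. It is not. That analysis (10.3) is of 6MW distance at 2 months with baseline 6MW as covariate, and breathlessness plays no part. Section 10.4 sets no decisive time point for the other continuous outcomes.

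**Conclusion.** The mismatch is real but narrow. The one-item shortness-of-breath question is scheduled at 0 of the 2 later visits in both questionnaire versions, while pain and FACIT-F are scheduled at 2 of 2. As written, the dedicated item supports a between-arm comparison at discharge only. Because the standard and short forms share the blank, this applies to every patient.

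The conclusion concerns the item and rests on the tables being the operative schedule. Whether the endpoint as such goes unmeasured at 2 and 6 months depends on the content of FACT-L and PROMIS, which the documents do not give. Whether the blanks were intended cannot be settled either; the pattern across rows leans towards an omission without proving one. The importance is low: an exploratory symptom, no effect on the primary endpoint or its power, and a cheap improvement available.

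**What to change.** Add the single shortness-of-breath item to the 2-month and 6-month columns of row 49 in both 7.1 and 7.2, as is already done for pain. For patients already past those visits, report the item as available at discharge only.

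If another scheduled instrument is meant to supply this endpoint, name the instrument and its time points in 1.2.2 and 9.2 before analysis, so that the choice of measure is not made with the data in hand.

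The cost is one more question at two existing visits, on questionnaires already being given, and an amendment to the tables. The drawback is that 2-month and 6-month values will exist only for later patients. The documents do not say how many have already passed each visit, so the size of that subset is unknown. The report should state it, by arm, next to any comparison. The item should be introduced on the same date in both arms.

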7.2 Short Form Questionnaires

Concept/ Instruments	# of Items	Standard of Care (-2)	Pre-surgery (-1)	Discharge (1)	2 month (2)	6 month (3)
1. Physical activity/ Motivation						
2. BREQ-3	24	24		24	24	24
3. 7-day physical activity recall phone interview	12		12		12	12
4. 7-day physical activity recall phone interview calendar	N/A		X		X	X
5. PEP Exercise Diary	N/A		X	X	X	X
6. Overall Health						

7. FACT-L	36		36	36	36	36
10. Function						
11. AM-PAC outpatient short form	12		12	12	12	12
12. Activities of daily life (in WHI lifestyle questionnaire)	7		7		7	7
13. Lifestyle						
16. Personal Habits						
17. Weight change	2		2			
18. Physical activity/ exercise, asks about the usual physical activity and exercise	3		3		3	3
19. Marijuana – ColoCare Q	1				1	
20. Smoking history	11		11			
21. Smoking follow-up	11				11	11
22. Exercise confidence	11				11	
25. Self-Efficacy						
26. Self-Efficacy (Sallis, [name] recommended)	12	12		12	12	12
27. Affect						

28. Modified Differential Emotion Scale (mDES), Emotion experience during the past 24 hours	20	20		20	20	20
30. Social factors						
31. Social Support for Exercise (Sallis)	13	13		13	13	13
32. Subjective Social Status Ladders	2		1 out of 2		1 out of 2	1 out of 2
33. Financial Strain – COST	8		8			8
35. Loneliness (Cacioppo)	3	3		3	3	3
36. Demographics						
37. Education – ColoCare Q	1		1			
38. Marital Status – ColoCare Q	1		1			
39. Income – ColoCare Q	1		1			
40. Weight	2		2		2	2
41. Height-ColoCare Q	1		1			
42. Ethnicity	3		3			
43. Sex	1		1			
44. Birthday	1		1			

47. Symptoms						
48. Pain	1	1	1	1	1	1
49. Shortness of breath	1	1		1		
50. Fatigue (FACIT-F)	13		13	13	13	13
51. Living condition (nursing home, relationship etc.)						
52. WHI – Lifestyle questionnaire	3		3		3	3
53. Others						
54. PROMIS Score (Dimensions)	CAT	Clinic-based assessment				
55. Saliva Questionnaire	9					9
56. Blood Questionnaire	5		5		5	
57. COVID-19		Completed as needed during outbreak				

8 STUDY PROCEDURES

8.1 Pre-Surgery Clinic Visit

During their pre-surgery clinic visit (which typically takes place 2-4 weeks prior to surgery as long as surgery is not delayed), all potential lung cancer patients who are surgical candidates (as determined and approved by the surgeon) will be approached about the PEP study. Enrollment may be postponed, and the decision to do so is dependent on all three principal investigators' discretion. This visit may be completed 1 week or up to 6 months prior to surgery depending on the health of the patient and surgical policies. This window may increase if patient and surgical policies require it. Patients who are interested and potentially eligible will undergo the following procedures either in the clinic space or at the Population Sciences (HOPE) clinic located in HCI Research North. All procedures listed below can, as is practical and applicable, also be performed by the study team and participants via telephone, text, email, snail mail, and/or MyChart:

- Informed consent. Consenting may be performed remotely, via phone, video chat, mail and/or email in situations where study staff is unable to consent in person. A copy of the signed consent form may be mailed or emailed to the participant. The process for consenting when unable to do so in person will include the following:
 - A brief introduction of the study from the treating surgeon.
 - Study staff will be notified of the potential participant from the treating surgeon or their clinic staff.
 - The research staff will attempt to contact the potential participant by phone to introduce the study. An email, text message, or message through MyChart may be sent if the patient does not answer.
 - Once the potential participant is reached by phone, the research team will discuss the study and email, mail, or send the consent form via MyChart if the patient is interested.
 - The patient will be given directions to sign the consent form (either personally or electronically) and email the signed copy back to study staff. Study staff will sign then sign the consent form upon receipt.
 - A copy of the signed consent form will be emailed, mailed, or sent through MyChart to the participant.
 - Study staff will coordinate a day and time to meet with the participant to perform study procedures that are required in person. Any procedures that may be completed remotely can be completed before the scheduled date and time.
- Verification of the patient's eligibility for the study. The enrolling physician may sign the eligibility criteria via email, if necessary, however staff will try to receive their signature in person.
- Randomization. This may be completed remotely.
- Baseline assessments by study staff including:
 - Body measurements (height, weight, waist and hips measurements). Staff will attempt to complete the body measurements in clinic, however the participant

may perform the measurements themselves at home. A measuring tape with the form to document the measurements may be mailed, emailed, via MyChart or provided to the participant directly. The participant may then perform the measurements themselves then return the form to staff via a prepaid envelope, email or via MyChart.

- Medical history, medication use. (reviewed and assessed by clinic staff)
- AM-PAC mobility score (via the AM-PAC outpatient form). Staff may perform the AM-PAC with the participant via phone (remotely), if the form cannot be given in clinic.
- 6 Minute Walk Test (6MW) and Short Physical Performance Battery (SPPB). Efforts will be made to ensure consistent 6MW and SPPB testing conditions throughout data collection for each participant, but some modifications may be necessary during the COVID19 pandemic. These results may be mailed, emailed, sent via MyChart or recorded verbally via the video platform.
- Baseline questionnaires and PROMIS (all patients – details in Section 7). The PROMIS may be completed up to 1 week before and 3 weeks after the presurgery clinic visit. Staff will attempt to have PROMIS completed in clinic, but may mail, email, send through MyChart or perform it via phone either on site or remotely. The follow-up questionnaires may be mailed before or after the visit or given to participant at the visit. Participants then may take the questionnaires home to be completed and returned the following weeks after the visit. Participants may also complete the questionnaire via phone with study staff (either on site or remotely) after being seen in clinic if they wish. The questionnaires may also be sent via email, mail, or the participant's electronic medical record (MyChart). Staff will remind participants at least once to complete and return the questionnaire. It will not be considered a deviation if the questionnaire is not received as long as an attempt to remind the participant has been made.
- Standard-of-Care (SOC) questionnaire (completed by all clinic patients regardless of participation in study). This questionnaire and the baseline questionnaire may be completed on the day of the pre-surgery clinic visit up to the day of surgery. Staff will remind participants at least once to complete and return the questionnaire. It will not be considered a deviation if the questionnaire is not received as long as an attempt to remind the participant has been made.
- 7-Day Physical Activity Recall (completed via phone or remotely for baseline). This may be completed up to 2 weeks before visit. It will not be considered a deviation if the 7-Day Physical Activity Recall is not received as long as three attempts are made.

Patients randomized to Group 1 will also receive the following:

- Exercise packet (with exercise tool), instruction for access to supplementary instructional video (if needed), tracking diary/calendar, the group 1 welcome letter, the 'Making Exercise Happen' factsheet, 'PEP Team Introduction' and activity tracker for

the home-based pre-surgical exercise program. The tracking diary/calendar results may be given to participants who request it. The tracking diary/calendar and exercise packet may be sent via email, mail, or the participant's electronic medical record (MyChart). It will not be a deviation if a participant does not return their diary as long as staff attempts to remind the participant to return it or if the participant declines to do it. The activity tracker may be mailed to the participant if staff is unable to provide it in clinic.

- Individual instruction by physical therapist (verbal and written) about the individual exercise modes and dosages to be performed at home and first PEP intervention. This may be administered in person, via phone, email, video chat, or remotely.

Patients randomized to Group 2 will receive the Group 2 welcome letter, 'Making Exercise Happen' factsheet, and the 'PEP Team Introduction' forms in person, mail, email, or MyChart.

Staff may forego any of the above procedures if clinic policy does not allow it (e.g. illness, virus outbreak, etc.).

If patients request to receive study materials and measurement results, the following may be given, mailed, emailed, or sent via MyChart:

Copy of exercise diary, 6MW, and their body measurements.

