8.2 In the Weeks Leading to Surgery (Outpatient)

During the time before the surgery, patients randomized to Group 1 will complete a daily PEP intervention as instructed by the physical therapist and record their activity on the tracking diary/calendar. The window before surgery may increase or decrease dependent on whether the patient is clinically and physically ready for surgery, as well as current surgical policies.

Weekly telephone calls or TeleHealth interactions (including video chat) between the patient and the study team will take place to answer questions, review exercise tracking/diary, and optimize patient engagement. Ongoing monitoring of attitudes and barriers to exercise will occur and strategies for encouraging uptake of the exercise intervention will be individually tailored. If needed, adjustments to the mode/dose of the exercise regimen will be made at the discretion of the physical therapist. These weekly phone calls may either be delayed or unsuccessful dependent on the participant's schedule, availability and whether or not they answer. However, study staff will make an effort to reach the participant if the participant continues to not answer or return the phone calls. In instances where a participant has felt burdened by these phone calls, research staff may perform the calls less frequently for these participants to maintain patient retention. Study staff may utilize text messaging and/or email in order to remind participants of future appointments/calls or to coordinate a day and time to reach the participant by phone. Study staff may also text and/or email the participants to send reminders, scheduling study procedures, etc..

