10 STATISTICAL CONSIDERATIONS

10.1 Randomization

Randomization will have a uniform 1:1 allocation ratio with block sizes of 8. The random allocation sequence will be stratified by the mobility staging (high vs. low) provided by the pre-treatment AM-PAC stage and whether it is a primary or secondary lung cancer diagnosis, based on primary data (as described in section 2.4), the AMPAC stage is sufficient to assess physical function.

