10.3 Primary Endpoint Analysis

Analyses will include all patients that are evaluable for our primary endpoint (expected at least $n=150$). The primary outcome will be the group effect for an analysis of covariance model with 6MW test at 2 months post-surgery as outcome and pretreatment 6MW test as covariate, tested at the nominal two-sided 0.05 significance level. A sensitivity analysis will be performed with additional adjustment variables (listed as covariates in Section 10.1). Missing data will be handled using multivariate imputation by chained equations⁸⁸ as implemented in the R package “mice”.

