10.4 Other Endpoint Analyses

The approach to testing for group differences for each continuous outcome (e.g., quality of life and fatigue summary scales, length of stay after surgical resection, cost) will be to test for the group effect in an analysis of covariance model with adjustment for covariates listed in Section 10.1 as well as baseline values of the outcome variable when available.

Cost data and utilization data are typically positively skewed with some patients having very high costs/utilization. To reflect the distributions of cost and utilization, a generalized linear regression (GLM) with log link and gamma distribution and the generalized beta of the second kind (GB2) will be applied. To examine health care utilization, a Negative Binomial Regression (NBR) will be used to handle over dispersion of patient visits.

The proportion of patients who continue to smoke post-surgery is expected to be too small to include as a reliable adjustment variable or outcome ($\sim 5\%$).⁸⁹ Former smokers will be tested (saliva) at the 6 month clinic visit to assess smoking recidivism. A separate descriptive analysis will be performed in the subset of smokers.

An analogous approach will be used for endpoints coded as binary variables (complications, readmission) using logistic regression models instead of analysis of

covariance models. If diagnostics plots show significant deviation from model assumptions, then a separate sensitivity analysis will be performed using appropriate robust regression methods such as those available in the “robust base” package in R.

The study design provides 96% power to detect a 10 point increase in FACT-L in the Intervention Group compared to the Control Group, similar to the effect of aerobic training on FACT-L reported in Jones.⁴⁶

Bland-Altman analysis will be used to analyze agreement between remote and in clinic 6MW and for calculation of 95% confidence intervals on limits of agreement. The intra-class correlation coefficient will also be reported. Gaussian linear regression models will be used to determine whether remote 6MW and other covariates listed in Section 10 can be used to predict in clinic 6MW. Cross-validation will be used to evaluate performance.

Gaussian linear regression models will be used to assess the ability to predict 6MW from covariates listed in Section 10.1 and previous 6MW. Cross-validation will be used to assess the performance.

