11 REGISTRATION GUIDELINES

Patients must meet all of the eligibility requirements listed in Section 5 prior to registration.

Patients must not have any study procedures or begin protocol treatment prior to registration.

Randomization to the Intervention or Control Arm will be done at the time of enrollment by the enrolling coordinator using OnCore (the Clinical Trials Office’s electronic clinical research management system).

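### Baseline questionnaires and PROMIS may be completed after Group 1 has begun exercising, yet Section 10.4 adjusts for them as baseline values

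*Combined protocol and SAP*

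**What the plan says.** **Start of the intervention.** Under Section 11, randomisation takes place at enrolment. Section 8.1 includes the first PEP session among the pre-surgery visit procedures for Group 1. Under Section 8.2, in the time before surgery, "patients randomized to Group 1 will complete a daily PEP intervention as instructed by the physical therapist". Section 8.1 puts the visit typically 2 to 4 weeks before surgery, but allows 1 week to 6 months, with further extension possible.

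**Collection of the baseline forms.** Of the SOC form, Section 8.1 says: "This questionnaire and the baseline questionnaire may be completed on the day of the pre-surgery clinic visit up to the day of surgery". On PROMIS it says: "The PROMIS may be completed up to 1 week before and 3 weeks after the presurgery clinic visit". By the Section 7 tables, the SOC form carries BREQ-3, self-efficacy, mDES, social support for exercise and loneliness. The pre-surgery form carries FACT-L, FACIT-F and, in the standard version, PSQI. Pain is on both.

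**Use of the values.** Section 10.4 tests each continuous outcome by analysis of covariance, adjusting for the listed covariates "as well as baseline values of the outcome variable when available". The covariate list in Section 10.2 (which 10.3 and 10.4 cite as 10.1) includes pain and sleep, so both also enter the sensitivity analysis of the primary endpoint. No section says what to do with a baseline value dated after allocation.

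**The concern.** Adjustment for baseline is safe in a randomised trial because the covariate precedes allocation and cannot carry any treatment effect. A form filled in after days or weeks of PEP lacks that protection. Conditioning on it removes, or adds, part of the effect being estimated.

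The exposure is greatest where PEP acts most directly. Section 2.6 says the intervention aims to raise motivation and self-efficacy. BREQ-3 and the self-efficacy scale have their only pre-surgery administration on the SOC form, and Section 10.4 names self-efficacy as a possible mediator. FACT-L, FACIT-F, PSQI and PROMIS are named under Secondary Endpoint #2. Late completion is allowed by the protocol, so it would not be recorded as a deviation and would not be visible at analysis unless completion dates are kept.

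**Working it through.** **Inputs**
- FACT-L effect and power, Section 10.4: "The study design provides 96% power to detect a 10 point increase in FACT-L in the Intervention Group compared to the Control Group".
- Test level: the primary analysis in Section 10.3 is "tested at the nominal two-sided 0.05 significance level"; the same is assumed for FACT-L.
- Evaluable patients, Section 10.2: 200 × (1 − 0.25) = 150, or 75 per arm.
- Pre/post correlation r = 0.5: Section 10.2 gives it for the 6MW; borrowed here for FACT-L.
- Not in the documents: the FACT-L SD, the share of late forms, and the effect of PEP before surgery.

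**Step 1: the plan's 96%.** It cannot be reproduced without an SD, so I solve backwards.
- SE of the adjusted difference = 10 / (1.960 + 1.751) = 2.695.
- Residual SD = 2.695 / √(2/75) = 16.5.
- Total SD = 16.5 / √(1 − 0.5²) = 19.1.

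The SE follows from the 96% and the test level alone. The SD also needs 75 per arm and r = 0.5.

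**Step 2: bias.** Let m be the mean change in the Group 1 baseline caused by PEP, that is, the share of late forms times the mean early change among them. Then

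expected estimate = δ − b × m, with b = r × SD(post)/SD(pre) = 0.5 for equal SDs.

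Power ≈ Φ(estimate/2.695 − 1.960).

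**Step 3: range for δ = 10**

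| Mean early shift m | Estimate | Power |
|---|---|---|
| 0 | 10.0 | 96% |
| 0.6 (e.g. 25% late × 2.5 points) | 10 − 0.3 = 9.7 | 95% |
| 2 | 10 − 1.0 = 9.0 | 92% |
| 5 | 10 − 2.5 = 7.5 | 79% |
| −2.5 (opposite sign) | 10 + 1.25 = 11.25 | 99% |

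With r = 0.7 (also an assumption), the 5-point shift gives 10 − 3.5 = 6.5 and power of 67%.

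**Step 4: simulation check** (4,000 trials per scenario, SD 19.1, r = 0.5)
- No late forms: estimate 10.05, power 96.0%.
- Half of the forms late, with half the effect present: 8.77 and 89%.
- All late, with half the effect present: 7.49 and 78%.
- All late, with an opposite shift of a quarter of the effect: 11.26 and 99%.

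These agree with the formula.

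**The case against.** The strongest reply is that this is a permitted window of unknown use. The SOC form goes to all clinic patients whether or not they join the study, and many forms may be completed at the visit. A 5-point average shift needs, for example, every Group 1 form to be late with half the final effect already present. With few late forms the loss is a few tenths of a point. Under the trial's own hypothesis the bias is conservative. All of this stands and limits the size, but it does not make a value altered by treatment a valid baseline.

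A reader might infer more than the documents support:
- **That the primary analysis is biased**, because Section 8.1 lists randomisation before the 6MW. The list is not chronological: it also puts after randomisation items that may be completed 1 or 2 weeks before the visit. The covariate is specified as pretreatment 6MW and has no late window.
- **That stratified randomisation cannot be carried out.** Section 10.1 has it "stratified by the mobility staging (high vs. low) provided by the pre-treatment AM-PAC stage", and Section 11 says "Patients must not have any study procedures or begin protocol treatment prior to registration". Section 11 bars procedures before registration, not before randomisation. Consent, registration, AM-PAC and then randomisation satisfies both.
- **That the pre-anesthesia blood is adjusted for as baseline.** No section calls it baseline. That use could only be inferred from the general rule in 10.4, and biomarkers are exploratory.
- **That every patient-reported comparison is affected.** AM-PAC has its own item at the visit with no late window, the baseline 7-day recall may precede the visit by up to 2 weeks, and CTXD has no pre-surgery administration.

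**Conclusion.** The concern holds for the outcomes and covariates taken from the SOC and baseline questionnaires and PROMIS. Followed as written, the plan can adjust for values that the intervention has already changed, and it has no rule to prevent this.

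The direction is conditional. It is towards zero if the pre-surgery effect has the same sign as the later one, and away from zero if, for instance, early soreness worsens the scores. The FACT-L figures, a loss of about 0.3 to 2.5 points out of 10, are an illustrative range. They rest on a back-solved SD, a borrowed correlation and assumed shifts, and are not a prediction.

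The primary 6MW comparison is not shown to be affected. Its sensitivity analysis is exposed through pain and sleep if those are the pre-surgery questionnaire values; Section 10.2 does not give their timing. The change should be made before analysis, but the concern does not call the primary result into question.

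**What to change.** 1. **Section 8.1:** have the SOC and baseline questionnaires and PROMIS completed before the arm is disclosed or, at the latest, before the first PEP session. Record the completion date of each.
2. **Section 10.4:** state that a questionnaire or PROMIS value dated after randomisation is not used as a baseline covariate. Treat it as missing and impute it from pre-randomisation data, using the chained-equations method already planned in 10.3. Add a sensitivity analysis with the values as collected. Apply the same rule to pain and sleep in the 10.3 sensitivity analysis.
3. **Sections 8.3 and 10.4:** state that the pre-anesthesia blood is a post-randomisation measurement and not a baseline covariate.
4. **Sections 8.1 and 11:** state the order explicitly: consent, registration, AM-PAC, 6MW and SPPB, then randomisation.

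**Cost.** The change is mainly wording, but it has a burden. By the Section 7.1 item counts, the SOC form has 74 items and the pre-surgery form about 140 (without the recall and blood forms), so more than 200 in all before PROMIS. The first visit will be longer or need more reminders, and surgery may be only 1 week away. Some baseline values will be lost to imputation. For patients already enrolled, the analysis rule works only where completion dates exist.
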